5.11.3. Severe, Persistent Hyperglycemia

Frequency counts and percentage of patients initiating rescue therapies due to severe persistent hyperglycemia will be presented using ITT population. Fisher's exact test will be applied to compare treatments on the proportion of patients initiating rescue therapies due to severe persistent hyperglycemia. Time to initiating rescue therapies due to severe persistent hyperglycemia will be analyzed between treatment groups using semi-parametric proportional hazard Cox model with treatment and OAM usage as fixed effects, and baseline HbA1c as covariate. A Kaplan-Meier curve will be plotted for both treatments on the same graph, for presentation purposes. Listing of patients who experienced severe, persistent hyperglycemia will be provided.

5.11.4. Vital Signs

Vital signs (systolic blood pressure, diastolic blood pressure, and pulse rate) and their change from baseline will be summarized by descriptive statistics (mean, SD, median, standard error, min, and max) by treatment group and visit for the ITT population. The average values of the 2 measurements of each vital sign will be used for the analysis.

In addition, the MMRM model will be applied to evaluate the change from baseline in vital signs as the dependent variable with treatment, OAM usage, visit, baseline HbA1c strata (<8.5%, and $\geq 8.5\%$) and treatment-by-visit interaction as fixed effects, baseline vital signs as a covariate and patient as a random effect. The LS Means will be estimated using the observed margins (OM) option in SAS MIXED procedure.

The number and percentage of patients with treatment-emergent outlier vital signs at each post-baseline visit will be presented and analyzed using Fisher's exact test for systolic blood pressure, diastolic blood pressure, and pulse rate according to the categories as listed below:

- Low systolic blood pressure (≤ 90 mmHg and a decrease from baseline ≥ 20 mmHg)
- High systolic blood pressure (≥ 140 mmHg and an increase from baseline ≥ 20 mmHg)
- Low diastolic blood pressure (≤ 50 mmHg and a decrease from baseline ≥ 10 mmHg)
- High diastolic blood pressure (≥ 90 mmHg and an increase from baseline ≥ 10 mmHg)
- Low pulse rate (< 50 bpm and a decrease from baseline ≥ 15 bpm)
- High pulse rate (> 100 bpm and an increase from baseline ≥ 15 bpm)

5.11.5. *Electrocardiogram*

Count and percent of patients with a change in the ECG from baseline and with an ECG changes which is an adverse event will be analyzed using Fisher's exact test.

5.11.6. *Analysis of Laboratory Analyte*

A listing of all laboratory measurements including scheduled and unscheduled, by site and by visit, using all randomized patients, will be provided. A listing of all laboratory measurements that are outside the normal range will also be presented for. Certain laboratory measurements will be listed using clinical relevant thresholds other than laboratory limits.

All summary analyses will be conducted by treatment group, using ITT population. Descriptive statistics will be presented, by treatment group and visit, for the laboratory measurements.

For each continuous laboratory measurement, the change from baseline, at endpoint will be analyzed using ANOVA on ranks, with treatment as a fixed effect. Last-observation-carried-forward (LOCF) values will be used to impute missing post baseline values for the last visit. The incidence and percent of high, low and normal values will be listed for each of the treatment arms and compared using the Fisher's exact test. Shift tables for selected analytes using clinically meaningful thresholds will be summarized descriptively.

For subjective (qualitative) laboratory assessments, count and percent of normal and abnormal values will be analyzed using Fisher's exact test.

Counts and percentages for patients with pancreatic enzymes above upper limit of normal (ULN) and greater than or equal to $3 \times$ ULN will be summarized.

A summary of changes (shift tables using normal and abnormal categories) in amylase (total) and lipase evaluation from baseline to the maximum postbaseline will be produced.

Additional analyses will be conducted if deemed necessary.

5.11.7. *Pharmacokinetic/Pharmacodynamic Analyses*

Not applicable for this study.

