Vital signs (BP and PR ^e)	X	X	X	X	X	X		X		X		X		X		X	X	X	X	X
Electrocardiogram ^f	X																	X	X	
Preexisting conditions and adverse events	X	X	X	X	X	X	X ^g	X	X	X	X	X								
Concomitant medications	X	X	X	X	X	X	X ^h	X	X	X	X	X								
Review/record hypoglycemic events		-	X	X	X	X	X ⁱ	X	X	X	X									
Patient summary																		X	X	X
Patient Education																				
Dietary and exercise counseling and BG management training ^j		X	X																	
BG meter and SMBG training		X	X																	
SUP training and SoloStar pen training ^k		X	X																	
Dispense BG meter/supplies ^l		X	X	X	X	X		X		X		X		X		X		X		
Dispense study diary, instruct in use		X	X	X	X	X		X		X		X		X		X	X ^m	X		

	Screening/Lead In		Treatment Period															Safety Follow-Up	
			1	2	3 ^a	4	5	6	7	8	9	10	11	12	13	14	15	16	
Visit																			801
Week of Treatment	-3	-2	0	1	2	4	5	6	7	8	9	10	11	12	13	14	15	16	32
Allowable Deviation (±Days)	±7	±3	0	±3	±3	±4	±2	±4	±2	±4	±2	±7	±2	±7	±2	±7	±2	±7	±7
Fasting visit ^c			X									X					X	X	
Telephone visit							X		X		X		X		X				
Review and transfer to eCRF/return study diary				X	X	X	X		X		X		X		X	X	X		X
Remind patients about 7 point SMBG ^a		X								X						X			
Review/record 7-point SMBG values			X										X				X	X ^d	
Review fasting/4-point BG from SMBG ^f			X	X	X	X	X	X	X	X	X	X	X	X	X	X	X	X	
Review study drug usage			X	X	X	X		X		X		X		X		X	X	X	
Review insulin dose and adjustment per TTT algorithm ^g			X	X	X	X	X	X	X	X	X	X	X	X	X	X	X	X	
Dispense study drug and injection supplies			X			X				X				X					
Observe patient inject dulaglutide QW			X																
Patient returns study drug and injection supplies				X	X	X		X		X		X		X		X	X	X	
Assess dulaglutide compliance						X				X		X		X		X	X	X	
Assess compliance with weekly insulin dose adjustment per TTT algorithm					X	X	X		X ^e		X ^e		X ^e		X	X	X	X	
Laboratory tests																			
Serum pregnancy test ^a	X																		
Urine pregnancy test ^t			X													X	X	X	
Follicle-stimulating hormone test ^u	X																		
Chemistry panel	X															X ^v	X ^v		
Serum creatinine, eGFR (CKD-EPI) ^w	X		X													X	X		
Urinary albumin/creatinine			X													X	X		
Calcitonin	X		X													X	X		
Hematology	X															X	X		

	Screening/Lead In		Treatment Period															Safety Follow-Up	
			1	2	3 ^a	4	5	6	7	8	9	10	11	12	13	14	15	16	
Visit																			801
Week of Treatment	-3	-2	0	1	2	4	5	6	7	8	9	10	11	12	13	14	15	16	32

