Sitting BP and PR will be measured using standardized equipment provided by the Sponsor according to the Schedule of Activities (Section 2). Vital sign measurements should be taken before obtaining an ECG tracing and before collection of blood samples for laboratory testing, at visits where required (see Schedule of Activities Section 2). The patient should be allowed to sit quietly for 5 minutes before vital sign measurements. An appropriately sized cuff (cuff bladder encircling at least 80% of the arm) should be used to ensure the accuracy of BP measurements. The arm used for the BP measurement should be supported at heart level. At Visit 1 (screening), to determine which arm should be used to collect BP and PR throughout the study. BP and PR will be measured once in each arm and the arm that had the higher BP should be used to collect all 2 measurements of both BP and PR at all study visits. For each parameter (PR, SBP/diastolic blood pressure [DBP]), 2 measurements will be taken using the same arm; the recordings should

be taken at least 1 minute apart. Each measurement of sitting PR and BP is to be recorded in the eCRF. Any AE related to changes in BP and PR should be reported.

9.4.3. *Laboratory Tests*

For each patient, laboratory tests detailed in ([Appendix 2](#)) should be conducted according to the Schedule of Activities (Section [2](#)).

Any clinically significant findings from laboratory tests that result in a diagnosis and that occur after the patient receives the first dose of investigational product(s) should be reported to Lilly or its designee as an AE via eCRF.

9.4.4. *Body Weight, Height, and Body Mass Index*

Body weight will be measured at prespecified time points (see Schedule of Activities, Section [2](#)). Each patient's weight should be measured according to a standardized protocol. Body mass index will be computed from the patient's weight and height.

9.4.5. *Safety Monitoring*

Lilly will periodically review evolving aggregate safety data within the study by appropriate methods.

Specific safety measures are included in the protocol to ensure appropriate monitoring of pancreatic (Section [9.2.2.3](#)), thyroid (Section [9.2.2.4](#)), and liver safety (Section [9.4.5.1](#)).

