10.3.4.5. Vital Signs

The average value of the 2 sitting vital sign measurements will be used for analyses.

Descriptive statistic for the actual measurements and changes from baseline for SBP, DBP and PR will be presented by treatment and visit on the ITT population.

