 2. Injection site erosion
 3. Injection site erythema

4. Injection site hypersensitivity
5. Injection site induration
6. Injection site pruritus
7. Injection site exfoliation
8. Injection site vasculitis
9. Injection site photosensitivity reaction
10. Injection site rash
11. Injection site urticaria
12. Injection site hypertrophy
13. Injection site inflammation
14. Injection site irritation
15. Injection site oedema
16. Injection site warmth

For hepatic safety, apply the Drug related hepatic disorders - comprehensive search SMQ (20000006).

All AEs and treatment-emergent adverse events (TEAEs), defined as an event that first occurs or worsens (increases in severity) on or after first dose will be listed by patient and visit using MedDRA PT and SOC. Information on treatment, preferred term, reported term, severity, seriousness, and relationship to study drug will be reported. Listings of patients with study and study drug discontinuation due to AEs or death will be produced.

Summary statistics will be provided for TEAEs, SAEs, and study and study drug discontinuation due to AEs or death during the treatment period and through safety follow-up. Counts and proportions of patients experiencing AEs will be reported for each treatment group, and Fisher's exact tests will be used to compare the treatment groups.

Listings and summary statistics will also be provided for adverse event of special interest (AESI) including deaths, hypoglycemia, severe, persistent hyperglycemia, nonfatal CV events, adjudicated and confirmed pancreatitis, thyroid neoplasm, allergic and hypersensitivity reactions.

Since gastrointestinal (GI) AEs, like diarrhea, nausea, abdominal distension and vomiting, are among the most common events reported in patients treated with dulaglutide, summaries and analyses for onset, duration, and severity of diarrhea, nausea, abdominal distension and vomiting will be provided. The duration of an adverse event was calculated as adverse event end date minus the adverse event start date plus 1 day and was reported in terms of median number of days. Time to onset of an adverse event was analyzed by day, from the first dose date of the study drug to the occurrence of the adverse event.

The following PTs will be used to identify GIAEs:

1. Specific diarrhea symptoms include the following PTs
 - a. Diarrhea (10012735)
 - b. Fecal volume increased (10049939)

- c. Frequent bowel movements (10017367)
- 2. Specific nausea symptoms include the following PTs

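### Vital-sign outliers are counted and tested visit by visit only, so the plan never gives the number of distinct patients who met each criterion at any time

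*SAP*

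**What the plan says.** SAP 5.11.4 defines six treatment-emergent outlier categories: low and high for each of systolic pressure, diastolic pressure and pulse rate. Each combines an absolute threshold with a minimum change from baseline. One reads "High pulse rate (> 100 bpm and an increase from baseline" of at least 15 bpm. The comparison is set per visit, with Fisher's exact test: "The number and percentage of patients with treatment-emergent outlier vital signs at each post-baseline visit will be presented and analyzed using" that test. No count of patients meeting a criterion at any post-baseline visit is stated.

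The same section also plans descriptive statistics by arm and visit, and a repeated-measures model: "In addition, the MMRM model will be applied to evaluate the change from baseline in vital signs as the dependent variable". Protocol 10.3.4.5 is less ambitious: "Descriptive statistic for the actual measurements and changes from baseline for SBP, DBP and PR will be presented by treatment and visit".

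The row "Vital signs (BP and PR" in the Schedule of Activities (Protocol 2) reads as nine scheduled treatment visits after baseline: Visits 4, 5, 6, 8, 10, 12, 14, 16 and 17. Early termination and Visit 801 come on top. The table layout is damaged in the text available, so nine is a reading, not a certainty.

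Elsewhere the SAP does summarise across visits. Hypoglycemia incidence is given by visit, by period and overall (5.11.2). Total amylase and lipase are summarised at their maximum post-baseline value (5.11.6). Adverse events are compared between arms per patient (5.11.1): "Counts and proportions of patients experiencing AEs will be reported for each treatment group, and Fisher's exact tests will be used to compare the treatment".

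**The concern.** An outlier table is there to show how many patients had a marked excursion, and whether that number differs by arm. By-visit counts cannot answer this. They do not separate one patient with nine excursions from nine patients with one each, and they cannot be added up without double counting. The reader gets up to nine p-values per category, each resting on the few patients who were outliers on one day, and no overall result. A scattered excess may leave no visit significant. Conversely, one significant visit among nine is hard to interpret, because nothing controls for the repeated looks. Vital-sign change is a listed safety endpoint, and this is the only part of 5.11.4 aimed at individual excursions rather than means.

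**Working it through.** **The plan's own figure.** The documents size the trial for HbA1c only. With difference 0.5, SD 1.2, two-sided alpha 0.05 and 90% power, n = 2 × (1.960 + 1.282)² × 1.2² / 0.5² ≈ 121.04, so 122 per arm; the t-based value is 122.01, so 123. Power at 123 is about 90%, and 246 / 0.85 = 289.4, so 290 randomized. The stated figures reproduce. No rate, SD or power is stated for vital-sign outliers, so every rate, correlation and vital-sign SD below is an assumption.

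**Number of tests.** 9 visits × 6 categories = 54.

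**What one visit needs, with no assumed rate.** With 145 per arm, Fisher's two-sided p is 0.060 for 5 vs 0 and 0.067 for 7 vs 1. Significance takes 6 vs 0 or 8 vs 1 at the same visit. Suppose 1 vs 3 patients are outliers at each of nine visits, all different people. Every visit test gives p = 0.62, while the any-time count of 9 vs 27 gives p = 0.002.

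**Power.** Under independence the any-time rate is 1 − (1 − p)⁹. For 1% this is 1 − 0.99⁹ = 8.6%; for 3% it is 1 − 0.97⁹ = 24.0%. Correlated cases were simulated with a latent normal variable (2,000 trials per row, 145 per arm, significant in the direction of harm):

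| Per-visit rates | Within-patient correlation | One visit test | At least one of nine (unadjusted) | Any-time test |
|---|---|---|---|---|
| 1% vs 3% | 0 | 9% | 58% | 93% |
| | 0.3 | 10% | 57% | 84% |
| | 0.5 | 9% | 50% | 69% |
| | 0.7 | 9% | 44% | 52% |
| 2% vs 4% | 0 | 8% | 53% | 76% |
| | 0.3 | 9% | 51% | 57% |
| | 0.5 | 8% | 47% | 45% |
| | 0.7 | 9% | 42% | 35% |
| 2% vs 5% | 0 | 17% | 82% | 97% |
| | 0.3 | 17% | 77% | 86% |
| | 0.5 | 17% | 71% | 73% |
| | 0.7 | 17% | 65% | 59% |

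A second model, with a patient random effect on the logit scale (SD 0 to 2.5), gives for 1% vs 3% about 48-58% for at least one of nine and about 59-94% for the any-time test. Repeat runs move these by one or two points. With 123 per arm, 1% vs 3% and independent visits, the three figures are 6%, 43% and 88.5%.

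**Error rate with no true difference (random-effect model, either direction).** The at-least-one-of-nine flag is wrong in under 2% of trials at 1% per visit, about 9-10% at 2% and about 17-21% at 5%. The any-time test stays at about 3-4% at 2% and 5% per visit. A Bonferroni version of the nine visit tests is weaker than the any-time test in every setting tried.

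**Mean shift.** As a rough one-visit stand-in for the mixed model, with 123 per arm and an assumed SD of change of 8-10 bpm, a 4 bpm pulse shift has 88-98% power. With an assumed SD of 12-14 mmHg, a 5 mmHg systolic shift has 80-90%.

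**The case against.** A reader might infer that a pulse-rate or blood-pressure signal would be almost undetectable. The documents do not support that. The mixed model in the same section uses all visits and would show a general shift. There is also an adverse-event route: "Any AE related to changes in BP and PR should be reported" (Protocol 9.4.2), and adverse events are compared per patient. That route is only partial, because Protocol 9.2.2.5 makes a vital-sign finding an adverse event when it is clinically relevant and leads to a diagnosis.

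A reader might also set the 8-9% power of one visit test against the any-time figure. That is not a like-for-like contrast: the plan runs nine tests per category, and about half of such trials would show at least one significant visit at 1% vs 3%. Nor are events discarded, since every outlier is tabulated at its visit. What is missing is de-duplication across visits.

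The any-time advantage is not universal. At higher rates with within-patient correlation the unadjusted flag is ahead: about 60% vs 49% for 3% vs 6% (random-effect SD 2.5) and 88% vs 81% for 5% vs 10% (SD 1.5). Part of that lead is bought with its inflated error rate.

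A third tempting step is to read 54 tests as 1 − 0.95⁵⁴ ≈ 94% chance of a false positive. That overstates the problem: it assumes independent tests that each use the full 5%, whereas Fisher's test on sparse counts uses much less.

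Finally, these are unpowered supportive tables that already exceed the protocol's descriptive plan, and SAP 5.2 allows further exploratory analyses. This limits the weight of the point but does not supply the missing count.

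**Conclusion.** The point holds as a gap in the safety summary. By-visit testing alone yields no per-category number of distinct patients affected and no single controlled comparison. What could be missed or misread is a modest excess of isolated extremes in different patients at different visits, with little mean change and no adverse-event report. The gain from an any-time test is large when outliers are rare and weakly correlated within patients. It shrinks with correlation, and at higher rates it disappears against the unadjusted flag. The argument that depends on no assumed rate is that the planned table cannot yield the number of affected patients. The power figures rest on assumed outlier rates and correlation, complete attendance at nine visits and 145 per arm. Neither the primary endpoint nor the sample size is affected.

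**What to change.** In SAP 5.11.4 add, for each of the six categories, the number and percentage of patients meeting the criterion at any post-baseline visit, each counted once, compared between arms by one Fisher's exact test (six tests in all). Use all post-baseline data. SAP 5.2 says that safety analyses are not censored after rescue or early discontinuation, and 5.11.4 states no exception, so the count should not be limited to on-treatment visits. Keep the by-visit counts as supportive output; whether to keep their p-values is optional.

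The cost is one sentence and one table from data already collected. One drawback needs handling: a patient seen more often has more chances to be counted, so unequal dropout can distort the comparison. Show the number of patients per arm with at least one post-baseline measurement, and read the result alongside discontinuation by arm.

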10.3.4.7. Laboratory Analyses

Laboratory measurements will be listed by patient and visit. An additional listing will be presented for laboratory measurements that are outside the normal range.

Laboratory measurements will also be summarized. For continuous (numeric) laboratory analytes, the change from baseline to endpoint will be analyzed using an ANOVA on the rank-transformed data, with treatment as fixed effects. Last observation carried forward will be used to impute missing post-baseline values.

For subjective (qualitative) laboratory analytes, counts and proportions of patients with normal and abnormal values will be analyzed using Fisher's exact tests.

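### Continuous laboratory changes are tested by rank ANOVA with treatment only; adding the baseline value as a covariate would give a more efficient test at no data cost

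*SAP*

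**What the plan says.** SAP 5.11.6 sets the comparison for continuous analytes: "For each continuous laboratory measurement, the change from baseline, at endpoint will be analyzed using ANOVA on ranks, with treatment as a fixed effect". Protocol 10.3.4.7 matches it: "the change from baseline to endpoint will be analyzed using an ANOVA on the rank-transformed data, with treatment as fixed effects". Treatment is the only model term in both. Missing values are handled in SAP 5.11.6 as follows: "Last-observation-carried-forward (LOCF) values will be used to impute missing post baseline values for the last visit".

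SAP 5.11.6 plans other laboratory outputs too. On categories it says "The incidence and percent of high, low and normal values will be listed for each of the treatment arms", with a Fisher's exact test. It adds shift tables at clinically meaningful thresholds, counts of pancreatic enzymes above the upper limit of normal (ULN) and at or above 3 times ULN, and shifts in total amylase and lipase, where a summary of the "evaluation from baseline to the maximum postbaseline will be produced".

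Elsewhere the SAP adjusts for the baseline value: HbA1c (5.6), body weight and FSG (5.7.2), SMBG (5.8.2), glargine dose (5.8.3), vital signs (5.11.4, "baseline vital signs as a covariate") and patient-reported outcomes (5.13).

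**The concern.** Change from baseline in laboratory measurements is a listed safety endpoint (protocol Section 4, SAP Table 4.1). The protocol gives pancreatic enzymes and calcitonin a stated purpose: to look for effects of dulaglutide (9.2.2.3 and 9.2.2.4). Subtracting baseline removes too much of it whenever r is below 1, so a plain change score is noisier than a comparison that estimates the baseline slope. In a safety comparison, extra noise means that a modest real shift is somewhat less likely to show. The baseline value is already collected and already used in most of the SAP's other continuous models, and neither document says why the laboratory model differs.

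**Working it through.** **The plan's own figure.** The only power calculation is for HbA1c (protocol 10.1, SAP 5.1): difference 0.5, SD 1.2, two-sided alpha 0.05, 90% power. The normal formula gives 2 × (1.960 + 1.282)² × (1.2/0.5)² ≈ 121, rounded up to 122 per arm. The t-based value is 122.01, rounded up to 123. Then 123/0.85 = 144.7, so 145 per arm and 290 in all, and 290/0.6 = 483. The figure reproduces but has no bearing on laboratory tests, for which no power, SD, effect size or correlation is stated.

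**Inputs for the check.** 145 per arm randomized and 123 per arm completing (SAP 5.1), 1:1 allocation, alpha 0.05 two-sided (SAP 5.2). Assumed: r from 0.3 to 0.9, equal variances at baseline and endpoint, and an effect sized so that the unadjusted change-score test on the raw scale has 80% power.

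**Variance.** With common variance σ²:

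- change score: 2σ²(1 − r)
- baseline-adjusted: σ²(1 − r²)
- ratio, adjusted to unadjusted: (1 + r)/2

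Power after adjustment is Φ[(1.960 + 0.842)/√((1 + r)/2) − 1.960]:

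| r | variance ratio | power, change score | power, adjusted |
|---|---|---|---|
| 0.3 | 0.65 | 80% | 93.5% |
| 0.5 | 0.75 | 80% | 89.9% |
| 0.7 | 0.85 | 80% | 86.0% |
| 0.9 | 0.95 | 80% | 82.0% |

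Example at r = 0.5: 2.802/0.866 − 1.960 = 1.275, and Φ(1.275) = 0.899.

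**Rank tests by simulation.** 145 per arm, 4,000 trials per row, same effect sizing. Lognormal rows use a log-scale SD of 0.5.

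| Data | r | rank ANOVA, change (planned) | rank ANCOVA, change | rank ANCOVA, endpoint |
|---|---|---|---|---|
| Normal | 0.5 | 77.3% | 87.3% | 87.4% |
| Normal | 0.7 | 79.0% | 84.1% | 82.4% |
| Normal | 0.9 | 77.7% | 79.2% | 76.2% |
| Lognormal | 0.5 | 79.0% | 85.5% | 87.8% |
| Lognormal | 0.7 | 76.9% | 80.7% | 82.5% |
| Lognormal | 0.9 | 76.9% | 77.4% | 77.5% |

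With no treatment effect (2,000 trials per row), all three tests rejected in 4.1% to 6.0% of trials.

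A separate lognormal run at 123 and 145 per arm, with unadjusted power near 77%, gave gains of about 7 to 11 points at r = 0.5, 3 to 6 at 0.7 and 1 to 2 at 0.9. The table puts the gain at r = 0.9 at 1.5 points or less, so 1 to 2 is best read as a ceiling. For skewed data, ranking the endpoint gains more than ranking the change at r = 0.5 and 0.7. For symmetric data at r = 0.9, ranking the endpoint loses 1.5 points against the planned test.

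**The case against.** The strongest case against is that nothing here is wrong. The analysed variable is the change, so each patient's baseline is used. Randomization protects the comparison, the type I error is held, and protocol and SAP agree. All of that stands.

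A reader might infer more: that the plan ignores baseline, that chance imbalance biases the result, or that real enzyme, calcitonin, lipid and renal effects will be missed. The documents support none of these.

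- Baseline is subtracted.
- Regression to the mean after a chance imbalance adds no bias on average over randomization; it is the efficiency loss described another way.
- The documents give no correlation or effect size for any analyte, so a loss cannot be asserted for four analyte groups alike.

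Safety detection also does not rest on this test. The categorical tests, shift tables and ULN counts do not depend on it. Protocol 9.2.2.4 has patient-level calcitonin rules, and 9.2.2.3 sends suspected pancreatitis to adjudication. These outputs do not fully replace the continuous comparison, since cut-offs at normal limits can miss shifts inside the normal range.

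The size depends on the set-up. The effects above shrink as r rises, to hold unadjusted power roughly constant. With one fixed lognormal effect (0.165 on the log scale, assumed; 123 per arm, 2,000 trials), the planned test already has 62%, 90% and 98% power at r = 0.4, 0.7 and 0.8. The gain from rank ANCOVA on the endpoint is then 15, 3.5 and 0.8 points. That is a fair limit on the benefit.

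One could add that vital signs are repeated measures under MMRM, while most laboratory panels have one scheduled on-treatment draw. That explains the absence of MMRM but not of a baseline covariate: the patient-reported outcomes in SAP 5.13 are also analysed at an LOCF endpoint, with the baseline score in the model.

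**Conclusion.** The point holds as one of efficiency. SAP 5.11.6 and protocol 10.3.4.7 use a valid test that does not adjust for baseline as a covariate, and a baseline-adjusted test is generally more precise. Near 77% unadjusted power, the gain is roughly 7 to 11 points at r = 0.5, 3 to 6 at 0.7, and at most 1 to 2 at 0.9. This rests on assumed correlations, assumed effect sizes and equal variances. For analytes that are stable within a patient, the change makes little difference in either direction. It does not touch the primary analysis, the error rate or the other laboratory safety outputs. Severity is minor: a free improvement.

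**What to change.** In SAP 5.11.6, replace the rank ANOVA with rank ANCOVA: rank the endpoint value as the response, with treatment and ranked baseline as model terms. Name the response explicitly, because ranking the endpoint and ranking the change give different results. The endpoint suits skewed analytes better; its price is about 1.5 points for a symmetric analyte at r = 0.9. Keep the Fisher tests, shift tables and ULN counts unchanged.

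Align protocol 10.3.4.7 and the matching Synopsis text, or record the change and its reason in the SAP. SAP 5.2 allows this without an amendment when no principal feature of the protocol changes. Make the change before unblinding. The cost is one covariate in the safety programs and no new data.

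### Laboratory high/low/normal values are tested between arms with no baseline condition, so abnormalities present before the first dose count as cases and no planned test compares new ones

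*SAP*

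**What the plan says.** All of the laboratory text is in SAP 5.11.6.

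- **Set:** "All summary analyses will be conducted by treatment group, using ITT population".
- **Categories of continuous analytes, by Fisher's exact test:** "The incidence and percent of high, low and normal values will be listed for each of the treatment arms and compared using the". No baseline condition, at-risk denominator or time point is given. The wording also does not settle whether high, low and normal form one three-way table or separate comparisons.
- **Qualitative assessments:** "count and percent of normal and abnormal values will be analyzed using" Fisher's exact test, again with no baseline condition.
- **Pancreatic enzymes:** "Counts and percentages for patients with pancreatic enzymes above upper limit of normal (ULN) and greater than or equal to" 3 x ULN are to be summarised. No test is stated.

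Three items in the same section do use baseline:

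- "For each continuous laboratory measurement, the change from baseline, at endpoint will be analyzed using ANOVA on ranks", with treatment as a fixed effect and LOCF for the last visit.
- "Shift tables for selected analytes using clinically meaningful thresholds will be summarized descriptively".
- "A summary of changes (shift tables using normal and abnormal categories) in amylase (total) and lipase evaluation from baseline to the maximum postbaseline" value, with no test stated.

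Elsewhere the SAP measures safety findings against baseline. SAP 5.11.4 counts "treatment-emergent outlier vital signs", and each category there needs both a threshold and a minimum change from baseline. SAP 5.11.1 defines a TEAE by first occurrence or worsening on or after the first dose. Neither document defines a treatment-emergent laboratory abnormality.

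**The concern.** The safety question for a laboratory category is whether more patients become abnormal on dulaglutide than on placebo. The test as written asks whether more patients are abnormal, whatever they were before. A patient who enters with a high value and stays high is a case in either arm and says little about the drug.

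Such patients can be enrolled. Protocol 6.2, criterion 18, excludes ALT only above 2.5 times the upper limit and admits patients with fatty liver disease within that limit. The exclusion criteria set no limit on lipase, amylase or lipids.

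What is at stake is the sensitivity of a supportive safety comparison. Randomisation balances baseline abnormality in expectation, so the test stays valid under the null. The question is how much of a real emergent difference it can see.

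**Working it through.** **Arm size.** SAP 5.1 gives 123 completers and 145 randomised per arm. This reproduces: 2 x (1.960 + 1.282)^2 x 1.2^2 / 0.5^2 = 121.04, so 122 per arm by the normal formula. The t-based value is 122.01, which rounds up to 123. Power at 123 is 90.4% (t-based 90.2%), and 246 / 0.85 = 289.4, so 290. The laboratory comparison has no stated figure of its own to reproduce.

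**Model.** Let b be the share abnormal at baseline, s the probability that an existing abnormality is still present, and e the rate of new abnormality among those not abnormal at baseline. The rate that the planned test sees in each arm is

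p = b s + (1 - b) e.

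With the same s in both arms, the between-arm difference is (1 - b)(e1 - e0). The term b s is common to both arms, so it also pulls the risk ratio towards 1.

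**Assumptions.** The documents give no laboratory rates. For illustration: e0 = 8%, e1 = 20%, s = 80% in both arms, 123 per arm, two-sided 0.05 (SAP 5.2), exact unconditional power of Fisher's test. The at-risk analysis uses 123(1 - b) per arm.

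| b | All patients, placebo vs dulaglutide | Difference | Risk ratio | Power as written | At risk per arm | Power, at risk |
|---|---|---|---|---|---|---|
| 10% | 15.2% vs 26.0% | 10.8 points | 1.71 | 49% | 111 | 68% |
| 20% | 22.4% vs 32.0% | 9.6 points | 1.43 | 34% | 98 | 62% |
| 30% | 29.6% vs 38.0% | 8.4 points | 1.28 | 24% | 86 | 56% |

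Example for b = 20%: 0.2 x 0.8 + 0.8 x 0.08 = 0.224 and 0.2 x 0.8 + 0.8 x 0.20 = 0.320. Among patients at risk the difference stays at 12 points and the risk ratio at 2.5.

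**Sensitivity to b and to arm size.** At b = 5% power is 60% as written and 70% at risk; at b = 2% it is 68% and 72%. At b = 0 the two analyses are the same. With 145 per arm, power is 57/40/29% as written and 76/70/65% at risk for b = 10/20/30%.

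**Sensitivity to equal persistence.** Suppose the drug also prolongs existing abnormalities, with s = 70% on placebo and 90% on dulaglutide. The all-patient differences become 12.8, 13.6 and 14.4 points for b = 10/20/30%. For b = 20%: 0.2 x 0.7 + 0.064 = 0.204 and 0.2 x 0.9 + 0.160 = 0.340. Power as written is then 65/62/62%, against 68/62/56% at risk. The gap closes and, at 30%, reverses.

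**Whole-distribution shift.** A simulation took a latent normal analyte, 123 per arm, 10-30% abnormal at baseline, within-patient correlation 0.6-0.8, and a shift that multiplies the emergent rate by 2.5. Power was roughly 43-98% as written and 43-95% at risk, close to each other within each scenario. The rank ANOVA on change from baseline had about 99% or more.

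**The case against.** The strongest reply is that the plan already has a between-arm test that uses baseline. The rank ANOVA covers each continuous analyte and is very powerful when the drug moves the whole distribution. A reader might infer from the categorical test that no baseline-aware laboratory comparison is tested; that is wrong. What stands of the concern is narrower. The rank test addresses the overall shift, and can miss a minority of patients who cross a limit while the rest do not move.

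A reader might also infer that the planned test hides harm in general. The documents do not support that. The loss depends on baseline abnormality rates that they do not give and on equal persistence in both arms. It is small when few patients are abnormal at entry, and it disappears under unequal persistence or a general shift.

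Nor should the enzyme threshold counts be read as losing power, because no test is planned for them. The normal/abnormal shift tables to the maximum postbaseline value already show new elevations of total amylase and lipase. What remains there is only that the counts mix pre-existing and new elevations.

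Finally, other safeguards work relative to baseline or screening: the hepatic triggers by baseline category (Protocol 9.4.5.1), the calcitonin rule (Protocol 9.2.2.4), and adverse-event reporting of clinically significant findings that lead to a diagnosis (Protocol 9.4.3). These reduce the consequence for individual patients. They do not supply a between-arm comparison of new laboratory abnormalities.

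**Conclusion.** The point holds in a limited form. As written, abnormalities present before the first dose count as cases in a tested comparison, contrary to the SAP's own rule for vital signs, and no planned test of laboratory values compares new categorical abnormalities between arms. With equal persistence the emergent difference is multiplied by (1 - b). Under the illustrative rates this costs about 19, 28 and 31 points of power (68 - 49, 62 - 34 and 56 - 24, from unrounded values) at 10, 20 and 30% abnormal at baseline. The rates and the equal persistence are assumptions, not facts about this trial. The change is worth making because it matches the test to the question and costs little. The primary endpoint, the key secondary endpoints, alpha and the sample size are not affected.

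**What to change.** In SAP 5.11.6:

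1. Define treatment-emergent high as not high at baseline and high post-baseline, and treatment-emergent low likewise. Use the baseline rule already in SAP 5.2 (Visit 3, or the last earlier value). Requiring only not high, or not low, keeps more patients than requiring a strictly normal baseline.
2. Run a separate Fisher's exact test for each. The denominator is patients at risk with at least one post-baseline value.
3. State the time point: any post-baseline value, or the last visit. For chemistry, haematology and lipids the choice matters little, since the Schedule of Activities plans post-baseline samples only at Visit 17 or early termination.
4. Keep the all-patient high/low/normal counts as a descriptive table, so that patients abnormal at baseline remain visible.
5. For the enzyme counts above ULN and at or above 3 x ULN, only add a breakdown by baseline status. No test is needed.

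The cost is SAP wording and a standard table, with no new data collection. The small downside is a denominator that differs by analyte and is smaller than the ITT set.
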